#### **7.4.1 Unanticipated (Serious Adverse) Device Effect [U(S)ADE]**

Unanticipated serious adverse device effect (USADE) refers to any serious adverse effect on health or safety or any life-threatening problem or death caused by, or associated with, a device, if that effect, problem, or death was not previously identified in nature, severity, or degree of incidence in the investigational plan or application (including a supplementary plan or application), or any other unanticipated serious problem associated with a device that relates to the rights, safety, or welfare of subjects.

### **7.5 Adverse Event and Device Deficiency/Device Malfunction Reporting**

#### **7.5.1 AE/ADE/UADE Reporting**

##### General AE Reporting

Safety surveillance and reporting starts as soon as the subject is enrolled in the clinical investigation. Safety surveillance and reporting will continue until the 12-Month follow-up visit has been performed, the subject is deceased, the subject concludes participation in the clinical investigation, or the subject withdraws from the clinical investigation. All adverse event data, including deaths and device deficiency data, will be collected throughout the time period defined above and will be reported to the Sponsor on a CRF. Additional information with regard to an adverse event should be updated within the appropriate CRF.

Except for those events listed in Section 7.6, AEs potentially related to the study procedure or AtriCure devices used in the study and other AEs that the PI determines as critical to safety evaluation will be captured on the eCRF. Standard medical terminology should be used when recording AEs.

In addition, the following information should be recorded:

- Onset Date
- Resolution date or date of death
- Intensity of the event
- Action Taken
- Outcome of the event
- Relationship of AE
- Indication of whether the event is serious

### 7.5.2 SAE/USADE Reporting

The investigator (or designee) must report all SAE/USADEs to the Sponsor via the Adverse Event CRF as soon as possible but no later than outlined below.

Clinical Site	Reporting timelines
All Sites	
SAEs must be reported to the Sponsor no later than 10 calendar days from the day the site personnel became aware of the event or as per the investigative site's local requirements, if the requirement is more stringent than those outlined.
 
An event determined by the Investigator to be life-threatening or to have led to death must be reported within 24 hours.

The date the site staff became aware the event met the criteria of an SAE must be recorded in the eCRF and ensure relevant source documents are collected. The Investigator will further report the SAE to the local IRB/EC according to the institution's IRB/EC reporting requirements. In the event of system outages or technical difficulties, serious and any unanticipated adverse events may be submitted via e-mail to [[contact]](mailto:[contact]). Upon availability of the system or resolution of the technical difficulties, the event will be recorded in the Adverse Event eCRF.

The Investigator (or designee) shall send a written report including a narrative description of the serious and/or unanticipated adverse event to AtriCure or their designee within three (3) working days of the initial report. The Investigator should follow all unresolved serious adverse events until the events are resolved, or the subject has exited the study, or the adverse event is otherwise explained.

AtriCure, Inc., or their designee, in cooperation with the Investigator, will assess all serious adverse events considered device-related for potential report-ability to the FDA as an Unanticipated Adverse Device Effect (UADE) in accordance with 21 CFR Part 812.46(b).

If a UADE determination is made, the Investigator and Sponsor will comply with UADE reporting requirements per 21 CFR Part 812.150. The Sponsor shall report the results of such evaluation to FDA and to all reviewing IRBs/ECs and participating Investigators within thirty (30) working days after the Sponsor first receives notice of the UADE. Thereafter the Sponsor shall submit such additional reports concerning the effect as FDA requests. Similarly, the Investigator shall submit to their reviewing IRB a report of any UADE as soon as possible, but in no event later than ten (10) working days, (or per local IRB requirements) after the Investigator first learns of the effect. The Investigator (or designee) shall provide documentation of the UADE report/notification sent to their IRB to AtriCure (or designee).

Note: It is also the responsibility of the Investigator to inform their IRB of other SAEs (i.e. non- UADEs) as required by their IRB/EC procedures and in conformance with FDA requirements.

If the subject reports any device or procedure related adverse events that are potentially serious during the follow-up evaluation period, the subject should return to the investigator's facility for further evaluation of the event.

### **7.5.3 Device Deficiency/Malfunction Reporting**

All device deficiencies/malfunctions should be reported on the appropriate CRF.

The investigator should report all device deficiencies/malfunctions to the Sponsor as soon as possible but no later than outlined below.

Clinical Sites	Reporting timelines
All Sites	Device deficiencies/malfunctions must be reported to the Sponsor no later than 10 calendar days from the day the site personnel became aware of the event or as per the investigative site's local requirements, if the requirement is more stringent than those outlined.

### **7.5.4 Adverse Event Reporting to Country Regulatory Authorities by the Sponsor**

The Sponsor will report SAEs and reportable device deficiencies/malfunctions to the country regulatory authority, per local requirements.

Clinical investigation SAEs and device deficiencies/malfunctions reportable per MedDEV 2.7/3 regulations will be submitted to European Competent Authorities by the Sponsor's Clinical Product Safety & Surveillance Group.

## **7.6 Expected Morbidity/Procedural Complications Reporting**

For purposes of this study, the following events occurring within 48 hours of study procedures are not considered reportable (not recorded on eCRF but recorded in source documents) as they are normally expected to occur in conjunction with surgical treatment for non-paroxysmal forms of atrial fibrillation procedures (Maze III) or are associated with customary, standard care of subjects undergoing cardiac surgery:

- Chest pain without associated ECG changes
- Post-operative/post-procedure pain
- Post-anesthesia emesis, nausea, or headache (within 24 hours of procedure)
- Electrolyte imbalance without clinical sequelae following procedure, even if requiring correction
- Pre - planned future surgical procedures
- Low grade temperature increase (101°F or 38.5°C)
- Dizziness: Imprecise term commonly used to describe various symptoms such as faintness, giddiness, imbalance, lightheadedness, unsteadiness or vertigo.
- Elevated white blood count, outside the standard laboratory normal value, without signs and symptoms of infection
- Post-operative hematocrit decreases from baseline measured in the OR, prior to the first incision, not associated with hemodynamic changes, remaining above 25% and requiring < 2 units PRBC's
- Minor, localized tenderness, swelling, induration, oozing, etc. at surgical site.
- Sinus bradycardia/tachycardia that does not require treatment or intervention
- Systolic or diastolic blood pressure changes that do not require treatment or intervention.
- Any blood transfusions during preplanned operative procedures and unrelated to an adverse event.
- Thrombocytopenia: does not become an AE until treatment is administered.

- Atelectasis - collapse of lung tissue affecting part or all of one lung; the alveoli are deflated. This is not considered to be an AE unless treatment other than chest PT is required or it prolongs hospitalization.
- Hyperglycemia - The use of insulin in the post-operative period does not constitute hyperglycemia if during the same hospitalization. An elevated blood sugar of less than 250 mg/dl during the first 48 hours post-operative does not constitute hyperglycemia.
- Pleural effusion is not an event unless treatment with thoracentesis or chest tube insertion is required
- Pericardial effusion without hemodynamic compromise or treatment
- Atrial Fibrillation /Atrial Flutter/Atrial Tachycardia with or without cardioversion.
- Junctional Rhythm requiring temporary pacing

*Note: Treated subjects will have received general anesthesia and therefore will also be subject to general anesthesia-associated complications and morbidity. These are also not considered reportable (recorded on eCRF) adverse events.*

*Note: This listing of events is intended to provide guidance to the Investigator and investigational site for the purpose of adverse event reporting. The Investigator should utilize his/her own clinical judgment in evaluating adverse experiences and may decide that the above events should be reported as adverse events based on the IRB/EC reporting requirements or the subject clinical situation.*

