## **4 ENDPOINTS**

### **4.1 Primary Safety Endpoint**

This composite safety endpoint includes surgical ablation procedure related to death, stroke (regardless of level of disability), myocardial infarction, and major bleeding events within 30-days of the index ablation procedure. Deaths beyond 30-days and through last follow up that are attributed to surgical ablation procedure or CRYOF would be reported as Major Adverse Events (MAEs).

All MAEs will be adjudicated by an independent physician, thus maintaining the objectivity of the primary safety endpoint. A detailed definition of the MAEs is provided below:

- Excessive Bleeding: is defined as a major complication if it is subsequent to a device related or study procedure-related injury and is treated with transfusion or results in a 20% or greater fall in HCT. Transfusion for anemia or other pre-existing condition that cause a fall in HCT without acute bleeding will not be considered a Major Adverse Event. Documentation of the cause of the bleed, and transfusion, and/or 20% or greater drop in HCT.
- Myocardial infarction (MI): When low blood flow causes the heart to starve for oxygen. Heart muscle dies or becomes permanently damaged. Documentation of MI; the presence of any one of the following criteria: (1) detection of ECG changes indicative of new ischemia (new ST-T changes or new LBBB) which persist for more than 1 hr, (2) development of new pathological Q waves on an ECG, and (3) imaging evidence of new loss of viable myocardium or new regional wall motion abnormality.

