#### **10.8.3 Independent Physician Adjudicator (IPA)**

An independent, non-investigator physician(s) will function as the adjudicator(s) under the direction of AtriCure, Inc. The physician(s) will be responsible for the review and adjudication of reported adverse events occurring up to 12-months post-procedure, including:

1. All Major Adverse Events listed under the primary safety endpoint;
2. All Serious Adverse Events;
3. All Unanticipated Device Effects;
4. All Adverse Events that are potentially related to the procedure or any of the AtriCure devices used in the study.

In addition, all primary safety endpoints and other adverse events determined by the adjudicator(s) to be relevant, will be adjudicated until the subject exits the study.

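### Section 7.6 can keep off the eCRF some early bleeds that Section 4.1 counts as major adverse events, which tilts the 15% safety comparison toward success

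*Combined protocol and SAP*

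**What the plan says.** Four parts of the protocol bear on this.

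- **Section 4.1 (Primary Safety Endpoint).** Excessive bleeding is an MAE if it follows a device-related or study-procedure-related injury and "is treated with transfusion or results in a 20% or greater fall in HCT". There is one carve-out: transfusion for anemia or another pre-existing condition that happens to "cause a fall in HCT without acute bleeding will not be considered a Major Adverse Event". Section 7.1.1 refers back to 4.1 for what counts as an MAE.
- **Section 7.6 (Expected Morbidity).** Listed events within 48 hours of study procedures "are not considered reportable (not recorded on eCRF but recorded in source documents". One item is a post-operative hematocrit decrease from the pre-incision value, "not associated with hemodynamic changes, remaining above 25% and requiring < 2 units PRBC's".
- **Section 7.5.1 (General AE Reporting).** The eCRF capture rule begins: "Except for those events listed in Section 7.6, AEs potentially related to the study procedure or AtriCure devices". The exemption therefore reaches events that may be related to the device or procedure.
- **Section 10.8.3 (Independent Physician Adjudicator).** The task is the "review and adjudication of reported adverse events".

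A note at the end of Section 7.6 calls the list guidance and lets the investigator decide to report a listed event.

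**The concern.** The same clinical episode can satisfy a primary endpoint definition and an exemption from recording. Nothing in 7.6 or 7.5.1 says which prevails. The hematocrit item also lacks a limit that a neighbouring item has: the item on transfusions during preplanned operations covers only those unrelated to an adverse event.

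The first 48 hours lie wholly inside the 30-day safety window. A qualifying bleed left off the eCRF drops out of the MAE numerator while the subject stays in the denominator. The error can run only toward meeting the 15% goal, and trial success requires that goal to be met (Section 8.10). Because reporting of listed events is left to judgment, up to 20 sites may also differ in what they enter.

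**Working it through.** **1. The two rules side by side**

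| Feature | Section 4.1 bleeding MAE | Section 7.6 hematocrit item |
|---|---|---|
| Cause | Device- or study-procedure-related injury | Not stated |
| Transfusion | Any amount qualifies | Exempt if under 2 units PRBC |
| Hematocrit | Fall of 20% or more qualifies | Exempt if it stays above 25% |
| Hemodynamics | No condition | Exempt only if no change |
| Time | Within 30 days | Within 48 hours |

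An episode falls under both rules if it follows such an injury, stays stable with hematocrit above 25%, needs 0 or 1 unit, and meets either limb of 4.1.

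**2. Where the limbs overlap**

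- *Transfusion limb.* One unit meets 4.1 and is under 2 units. The overlap exists whatever the size of the fall.
- *20% limb, relative fall.* The post-fall value is at most 0.8 × baseline and must exceed 25%, so baseline must exceed 25 / 0.8 = 31.25%. For example, 40% to 31% is a fall of 9/40 = 22.5%, and 31% is above the floor.
- *20% limb, absolute fall of 20 points.* Baseline must exceed 25 + 20 = 45%.

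Section 4.1 does not say whether the fall is relative or absolute. The documents give no distribution of baseline hematocrit, so the share of subjects above either threshold cannot be stated.

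**3. The plan's own safety design, reproduced**

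Inputs from Sections 8.2.2 and 8.3: n = 150, goal 15%, expected MAE rate 8.5%, exact binomial test, one-sided alpha 0.05, pass at 15 or fewer.

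- P(X ≤ 15 | n = 150, q = 0.15) = 0.0493.
- P(X ≤ 16 | n = 150, q = 0.15) = 0.0807, so 15 is the right limit.
- P(X ≤ 15 | n = 150, q = 0.085) = 0.794, which agrees with the stated 80% after rounding.

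**4. Effect of missed MAE subjects at a true rate of 15%**

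If k MAE subjects go unrecorded, the trial passes whenever the true count is at most 15 + k.

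| Missed subjects k | Effective limit | P(pass) at true 15% |
|---|---|---|
| 0 | 15/150 | 0.049 |
| 1 | 16/150 | 0.081 |
| 2 | 17/150 | 0.124 |
| 3 | 18/150 | 0.181 |

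The same can be put as a share f of MAE subjects missed, so that the recorded rate is 0.15 × (1 − f). P(pass) is 0.080 at f = 5% and 0.126 at f = 10%. The two views agree: 0.15 × 150 = 22.5 expected MAE subjects, and 10% of these is 2.25. Both k and f are assumptions; the documents give no figure for either, and zero is possible.

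**The case against.** The strongest reply is that the rules have different targets. Section 7.6 lists things normally expected after cardiac surgery, and its item names a hematocrit decrease, not bleeding after injury. Section 4.1 excludes transfusion for anemia without acute bleeding, and Appendix III separately defines hemodilutional anemia from bypass. On this reading 7.6 removes post-bypass drift and leaves injury bleeds alone. A site may well read it so, but no sentence requires it, and 4.1 uses the same laboratory change as evidence of an endpoint event.

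Other safeguards narrow the gap:

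- **Recognised injuries.** A reader might infer that an overt injury, such as an ablation-related atrial tear with a one-unit transfusion, would be hidden from the adjudicator. The documents do not support that. Atrial tear is its own term in Appendix III and is not on the 7.6 list. As a procedure-related event it goes on the eCRF under 7.5.1 and is adjudicated under item 4 of 10.8.3.
- **Serious events.** Section 7.5.2 requires SAE reporting and makes no exception for 7.6. But 4.1 does not require seriousness, and a stable one-unit bleed need not be an SAE.
- **Investigator judgment.** The note in 7.6 permits reporting. It does not oblige it.
- **Source documents.** Exempt events remain there, and Section 10.5 provides for monitoring of completeness. Retention makes recovery possible but does not put the event before the adjudicator.

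Finally, the 4.1 composite names major bleeding, and Appendix III defines Major Bleeding much more strictly, for example 4 or more units or a hemoglobin drop of at least 5 g/dL. If that definition governed, the overlap would nearly vanish. Sections 7, 7.1.1 and 8.2.2 all refer the endpoint to 4.1, which favours the 4.1 text, but the two definitions need to be reconciled.

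**Conclusion.** The conflict is real but narrow. It concerns a qualifying bleed in the first 48 hours that appears only as a stable hematocrit fall or a one-unit transfusion, with no separately reported injury. Such an event can stay off the eCRF in line with 7.6 and 7.5.1 although it meets 4.1.

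The direction is certain: any loss favours meeting the goal. The size is not known. One missed MAE subject is enough to lift the type I error from 0.049 to 0.081, above the planned 0.05; the documents give no ground for saying how many would be missed, or that a particular share of the MAE rate is at risk. The conclusion rests on the 4.1 bleeding definition governing. The hematocrit-fall limb also depends on whether 20% is relative or absolute; the transfusion limb does not.

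This should be fixed, because it affects a primary endpoint and the repair is small. It does not call the stated sample size, pass limit or power into question.

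**What to change.** Add to Sections 7.6 and 7.5.1, and to the CRF completion guidelines if these are developed, that the exemptions do not apply to any event that meets or may meet an MAE definition in Section 4.1. For bleeding, repeat 4.1's own scope: injury related to the device or to the study procedure, with transfusion of any volume or a hematocrit fall of 20% or more. The sentence should not be confined to ablation-related injury, which could be read more narrowly than 4.1. State that such events are entered on the eCRF from source documents and sent for adjudication.

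In the same edit, say whether the 20% fall is relative or absolute, and whether 4.1 or Appendix III defines the bleeding component.

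The cost is a sentence or two. The early data are abstracted retrospectively from medical records (Section 6.2.1) and exempt events are kept in source documents, so the rule can also be applied to subjects already enrolled. The downside is a few more events to adjudicate and possibly a slightly higher MAE rate. Sample size, pass limit and subject care do not change.

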## **7.7 Product Complaints**

A product complaint is any written electronic or oral communication that alleges deficiencies related to the identity, quality, durability, reliability, usability safety, or performance of a device after it is release for distribution (a medical device that has been released from the organization's control or related to a service that affects the performance of such medical devices). Product complaints may or may not be associated with an AE.

### **7.7.1 Reporting Product Complaints**

All product complaints (as defined above) related to an investigational product (shall be documented throughout the clinical investigation and appropriately managed by the sponsor. All reported device observations, malfunctions or failures for the cryoICE® cryoablation system are required to be documented in the EDC within 10 days of observation of the Product Complaint and sent via e-mail to [[contact]](mailto:[contact]) by the PI or study staff.

If the cryoICE® cryoablation system or component is involved in a complaint, the device should be returned to AtriCure (e.g., product is damaged or use results in an AE). If this occurs, sponsor representatives will send a Used Product Return Kit to study site personnel for packaging the product; which (depending on the product) may be sent to the appropriate facility for decontamination and further investigation of the complaint.

### **7.7.2 Reporting Product Complaints with Non-Investigational Device Products**

All reported device observations, malfunctions or failures for AtriCure Non-Investigational (i.e. Marketed Products) are required to be documented in the Clindex database on the device observation eCRF and emailed to [[contact]](mailto:[contact]) within 10 days of the observation by the PI or study staff.

If an event involving an AtriCure device is subject to reporting under the Medical Device Reporting Regulation (MDR), AtriCure shall submit to the FDA the appropriate reports required by MDR within the timeframes identified in 21 CFR Part 803.

### **7.7.3 Non-AtriCure Product Complaints**

In compliance with the requirements of 21 CFR Part 803.30 (MDR), the study site (user facility) will be instructed to report any SAEs associated with the use of other (non-AtriCure) marketed products/devices in this study to the respective manufacturer and, if the SAE involves a death, the complaint should be reported to the manufacturer.

### **7.7.4 Reporting Product Complaints for Global Compliance**

If a Product Complaint is reported in conjunction with a SAE/UADE, reporting guidelines will be the same as those listed in Section 7.5.4.

## **8 STATISTICAL CONSIDERATIONS**

The following section describes the statistical methods for the clinical investigation. Additional details on statistical analyses, including justification of clinical investigation design, sensitivity analyses, pool-ability analyses, subgroup analyses, etc., may be maintained in a separate Statistical Analysis Plan.

### **8.1 Analysis Populations**

#### Intention-to-Treat Population:

The Intention-to-Treat (ITT) population consists of the subjects on whom the CRYOF device was used. This is the primary population for performance and safety endpoints.

#### Protocol Population:

The Per-Protocol (PP) study population is defined by the ITT population but without any major protocol deviations, that is, those that could potentially bias the results. This population is defined for the primary performance endpoints.

### **8.2 Statistical Analyses**

The primary goal of the study is to demonstrate safety and performance of the CRYOF device. For the study to be successful, both endpoints must be statistically significant relative to their respective performance goals.

Standard descriptive statistics will be used to summarize numeric variables, including the number of observed values, mean, standard deviation, median, minimum and maximum values. Summaries of categorical variables will include the number and percentage of observed values, at each level of the categorical variable. Baseline and demographic information, including age, gender, race, ethnicity, height, weight, BMI, and medical history will be summarized with standard descriptive statistics.

